For Part A, the primary immunogenicity goal of the study is to evaluate serum antibody (Ab) responses obtained 28 days after the third dose (Day 113 for unvaccinated SOT participants who receive the 3-dose regimen and Day 29 for previously vaccinated SOT participants) of mRNA-1273 in SOT recipients. Using the Ab threshold established from Study P301 (if available at the time of database lock), an additional exploratory analysis will be performed by measuring the proportion of participants with a serum Ab level at Day 57 for unvaccinated participants of 2-dose regimen), Day 113 (unvaccinated SOT recipients of the 3-dose regimen), and Day 29 (previously vaccinated SOT recipients who receive dose 3) greater than or equal to the Ab threshold of protection against COVID-19, with a 2 sided 95% CI using the Clopper Pearson method by cohort arm.

This study will monitor participants for a total of up to 12 months (12 months after the last dose of the vaccine for participants not receiving a BD or 6 months after their BD). The SOT participants who do not consent to receive a third dose of mRNA-1273 and healthy adult participants will be monitored for a total of 12 months after their second dose. Safety assessments will include solicited local and systemic adverse reactions (ARs) for 7 days after each dose; unsolicited AEs for 28 days after each dose; MAAEs; SAEs; AESIs; AEs leading to discontinuation from dosing and/or study participation (withdrawal) from dose 1 through the end of study; concomitant medications associated with AEs, MAAEs, or COVID-19 or SARS-CoV-2 infection; participant experience of COVID-19 symptoms; biopsy-proven organ rejection; safety laboratory assessments; vital sign measurements; and physical examination findings as presented in the applicable schedule of events (SoE).

From all unvaccinated SOT participants who receive 3 doses of mRNA-1273 (Group A2), blood samples will be collected at baseline (Day 1), Day 29 (28 days after dose 1), Day 57 (28 days after dose 2), Day 85 (dose 3), Day 113 (28 days after dose 3), Day 265 (6 months after dose 3), and Day 450 (12 months after dose 3).

From unvaccinated participants who receive 2 doses of mRNA-1273 (healthy adults [Group A5] and SOT recipients who decline to receive a third dose [Group A1]), blood samples will be

collected at baseline (Day 1), Day 29 (28 days after dose 1), Day 57 (28 days after dose 2), Day 209 (6 months after dose 2), and Day 394 (12 months after dose 2).

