
 • To evaluate the persistence of the immune response to 2 or 3 doses of 100 µg mRNA-1273, as assessed by the level of anti-SARS-CoV-2 Spike (S) specific binding antibody (bAb) through 1 year after dose 2 or dose 3 	
 • For all unvaccinated participants, the geometric mean (GM) value of anti-SARS-CoV-2 S-specific bAb on Day 1, Day 29 (28 days after dose 1), and Day 57 (28 days after dose 2) 
 ○ For participants receiving the 2-dose regimen, GM will be evaluated on Day 209 (6 months after dose 2), and Day 394 (1 year after dose 2) ○ For participants receiving the 3-dose regimen, GM will be evaluated on Day 85 (dose 3), Day 113 (28 days after dose 3), Day 265 (6 months after dose 3), and Day 450 (1 year after dose 3) • For all previously vaccinated SOT recipients, GM will be evaluated on Day 1 (dose 3), Day 29 (28 days after dose 3), Day 180 (6 months after dose 3), and Day 365 (1 year after dose 3) • For all unvaccinated participants, the geometric mean fold rise (GMFR) of bAb relative to Day 1 on Day 29 (28 days after dose 1), and Day 57 (28 days after dose 2) 
 ○ For participants receiving the 2-dose regimen, GMFR will be evaluated on Day 209 (6 months after dose 2), and Day 394 (1 year after dose 2) ○ For participants in the 3-dose regimen, GMFR will be evaluated on Day 85 (dose 3), Day 113 (28 days after dose 3), Day 265 (6 months after dose 3), and Day 450 (1 year after dose 3)

Objectives	Endpoints

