8.1. Sample Size

The study vaccine, mRNA-1273, is currently being evaluated in a pivotal Phase 3 efficacy, safety, and immunogenicity study in an adult population at high risk of COVID-19 disease (Study P301). Success criteria for early efficacy was met at the first interim analysis based on 95 adjudicated cases with a vaccine efficacy of 94.5% (95% CI: 86.5%, 97.8%; one-sided p value < 0.0001 of testing the null hypothesis of $VE \leq 30\%$). Study P301 is expected to provide immunogenicity data by which an Ab threshold of protection against COVID-19 will be estimated.

This current study, which aims to evaluate Ab responses following a second, third, or fourth (booster) dose of mRNA-1273 vaccine among kidney and liver transplant recipients, is expected to provide clinical data to determine whether vaccination with mRNA-1273 will induce vaccine response in this cohort of immunocompromised participants that is comparable to those of the participants in Study P301 and comparable to those of the concurrently assessed cohort of participants in this study with normal immune function.

With 200 SOT participants, if the true AE rate of biopsy-proven organ rejection is 3%, there is approximately >95% probability to observe at least 1 subject reporting such an AE.

The planned sample size of approximately 240 participants (220 unvaccinated or previously vaccinated participants who have had a kidney or liver transplant and 20 unvaccinated healthy participants) who receive 2-dose regimen and 3-dose regimens of 100 µg of mRNA-1273, or 100 µg BD regimen are expected to provide useful estimates of Ab response at Day 29 for previously vaccinated SOT recipients who receive dose 3 in Part A, and Day 113 for unvaccinated SOT recipients who receive the 3-dose regimen, at Day 57 for unvaccinated participants who receive the 2-dose regimen, and at BD-D29 for Part B participants (participants who receive a BD) (primary endpoints), respectively, for comparison to results from Study P301 (if available at the time of database lock). The healthy adult participants will be used primarily as a biological control for the CMI analysis. This study is designed for estimation purposes, and no between-group comparisons are planned.

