3. If the visit for the third dose (Day 85) is disrupted and cannot be completed at Day 85 -3/+7 days as a result of the COVID-19 pandemic (self-quarantine or disruption of study site activities following business continuity plans and/or local government mandates for “stay at home” or “shelter in place”), the visit window may be extended to + 21 Day 85. When the extended visit window is used, the remaining clinic study visits D92 (last dose + 7 days), D113 (last dose + 28 days), 6 month visit (last dose + 180 days), and 12 month visit (last dose + 365 days) should be rescheduled to follow the scheduled inter-visit interval from the actual date of the third dose. The timing of diary follow-ups and safety calls will not be adjusted. Additional safety calls every 4 weeks should be scheduled if there is a gap beyond 28 days between the last safety call and the last study visit. Participants who agree to receive a booster dose in Part B of the study will follow the schedule of events for Part B (see Table 10).

4. Safety follow-up via an eDiary questionnaire will be performed every 4 weeks from Day 127 to Day 239 and again from Day 279 to Day 419.
5. Safety follow-up via a safety telephone call will be performed every 4 weeks from Day 141 to Day 253 and again from Day 293 to Day 433.
6. Physical examination: A full physical examination, including height and weight, will be performed to determine eligibility prior to administration of vaccine dose on Day 1. Body mass index will be calculated only at the screening visit (Day 0). Symptom-directed physical examinations will be performed at Day 29, Day 57, Day 85, Day 113, Day 265, and Day 450. Any clinically significant finding identified during a study visit should be reported as an MAAE.
7. On each injection day before injection and again 7 days after injection, the arm that received the injection should be examined and the associated lymph nodes must be evaluated. Any clinically significant finding identified during a study visit should be reported as an MAAE.

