Recording of suspected AND confirmed organ transplant rejection ¹⁷	X	X	X	X	X	X	X
Recording of concomitant medications and nonstudy vaccinations ¹⁷	X	X	X	X	X	X	X
Recording of concomitant immunosuppressant medications ¹⁸	X	X	X	X	X	X	X

Abbreviations: AE = adverse event; AESI = adverse event of special interest; AR = adverse reaction; BD = booster dose; C = clinic visit; D = day; eDiary = electronic diary; ICF = informed consent form; MAAE = medically attended AE; NP = nasopharyngeal; SAE = serious adverse event; SC = safety (phone) call; SOTr = solid organ transplant recipients.

Note: In accordance with FDA Guidance on Conduct of Clinical Trials of Medical Products during COVID-19 Public Health Emergency (DHHS 2020), investigators may convert study site visits to home visits or telemedicine visits with the approval of the Sponsor.

1. A BD may be administered to all eligible participants who are currently enrolled in Part A or Part B provided there are no current contraindications for further dosing ([Section Error! Reference source not found.](#)). A participant who is currently in the Convalescent Period may come in for a BD-1 visit and receive a BD as long they are no longer symptomatic, and this includes the possibility for a Convalescent Visit Day 28 to overlap and be combined with a BD-1 visit. For eligible participants in Part A who are at least 4 months from completion of primary vaccination series who consent to receive BD, the study visit or follow-up 4 months after their last dose in Part A may overlap with BD-D1. In this case, a participant will need to come in for the BD-D1 visit at least 4 months after the last dose and then follow Part B.

2. Symptom-directed physical examination will be performed at the BD-Day 1. At visits BD-2 (BD-D29), and BD-3 (BD-D181), a symptom-directed physical examination may be performed at the discretion of the investigator. Any clinically significant finding identified during a study visit should be reported as a MAAE.
3. On dosing day before injection, the arm receiving the injection should be examined and the associated lymph nodes should be evaluated.

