## **2.2. Secondary Objectives**

The secondary objectives for Part A are the following:

- To evaluate the persistence of the immune response to 2 or 3 doses of 100 µg mRNA-1273, as assessed by the level of anti-SARS-CoV-2 Spike (S) specific binding antibody (bAb) through 1 year after dose 2 or dose 3
- To evaluate the persistence of the immune response to 2 or 3 doses of 100 µg mRNA-1273, as assessed by the level of nAb through 1 year after dose 2 or dose 3
- To describe the incidence of asymptomatic SARS-CoV-2 infection after mRNA-1273 vaccination in adult solid organ transplant (SOT) recipients and healthy adult participants with negative SARS-CoV-2 at baseline
- To describe the incidence of coronavirus disease 2019 (COVID-19) after vaccination with mRNA-1273 in SOT recipients and healthy participants
- To describe changes in liver and renal function through laboratory tests over time in SOT recipients after vaccination with mRNA-1273 vaccine
- To describe changes in immunosuppressant medications in SOT recipients after vaccination with mRNA-1273 vaccine

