#### **6.4.3. Secondary Analysis of Antibody-Mediated Immunogenicity Response**

For each participant group, the following evaluations will be performed at each time point at which blood samples are collected for immunogenicity, unless otherwise specified.

For each of the reported assay/test results, the following analyses will be performed for both Part A and Part B, unless otherwise specified:

- GM levels of SARS-CoV-2-specific bAb or nAb with corresponding 95% CI will be provided at each time point.
- GMFR of SARS-CoV-2-specific bAb or nAb with corresponding 95% CI will be provided at each post-baseline timepoint over pre-injection baseline at Day 1.

Proportion of subjects with fold-rise  $\geq 2$ , fold-rise  $\geq 3$ , and fold-rise  $\geq 4$  of serum SARS-CoV-2 specific antibody levels from baseline at each post-baseline time points will be summarized with 2-sided 95% Clopper Pearson CIs.

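### Booster takers leave the Part A schedule before the late persistence visits, so the planned 28-day, 6-month and 12-month antibody means compare changing sets of participants, and no same-participant comparison is committed to

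*Protocol*

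**What the plan says.** The secondary objective for Part A is persistence of binding and neutralizing antibody "through 1 year after dose 2 or dose 3" (SAP 2.2). For the three-dose regimen, Protocol Table 1 sets the late time points as "Day 265 (6 months after dose 3), and Day 450 (1 year after dose 3"). The two-dose and previously vaccinated groups have matching visits. These endpoints are written for all participants of a regimen, without reference to booster status.

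The schedule of events takes booster recipients off that path: "Participants who agree to receive a booster dose in Part B of the study will follow the schedule of events for Part B" (Table 7 footnote 3 and Table 8 footnote 3; Table 9 footnote 2 has the same rule). Table 10 footnote 1 adds that "a participant will need to come in for the BD-D1 visit at least 4 months after the last dose and then follow Part B". Table 10 draws immunogenicity blood only at BD-D1, BD-D29 and BD-D181. The synopsis sets follow-up as "12 months after the last dose of the vaccine for participants not receiving a BD or 6 months after their BD".

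On analysis, SAP 5.2 keeps every Part A participant in the Part A sets whether or not they go on to Part B. SAP 6.4.3 says "GM levels of SARS-CoV-2-specific bAb or nAb with corresponding 95% CI will be provided at each time point", and takes fold rises against Day 1. SAP 6.1 does not impute missing antibody results. It allows participants on one regimen to be combined whatever their booster status, and says that boosted and non-boosted participants *may* be analysed separately.

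**The concern.** A reader of a persistence table will look at the 28-day geometric mean, then at the 6- and 12-month means, and read the drop as waning. On this plan the 28-day mean includes participants who later took the booster, while the late means largely do not. The booster is an option for participants already in Part A, so who is missing late depends partly on choice. If that choice is related to antibody level, through immunosuppression for example, the drop reflects a change in who is measured as well as a change in titre. At stake is the interpretation of a stated secondary objective in a population where durability of response is a main question.

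**Working it through.** **The plan's own figures.** The documents give no calculation for the persistence endpoints. The only numerical design statement (Protocol 8.1) is a probability above 95% of seeing at least one rejection among 200 SOT participants at a 3% rate. It reproduces, 1 − 0.97^200 = 0.998, but has no bearing here.

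**Step 1: when the booster falls.** Booster days are from Table 10, visit days from Tables 7 to 9.

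| Group | Last dose | Booster | 6-month visit | 12-month visit | Booster, days after last dose | Days before 6-month / 12-month visit |
|---|---|---|---|---|---|---|
| A2, three doses | D85 | D205 | D265 | D450 | 120 | 60 / 245 |
| A3, previously vaccinated | D1 | D120 | D180 | D365 | 119 | 60 / 245 |
| A5, healthy | D29 | D149 | D209 | D394 | 120 | 60 / 245 |

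An on-schedule booster taker supplies neither late Part A sample. (Protocol 3.1.1 and the synopsis give D129 for the healthy booster, 100 days after D29; this must be reconciled with Table 10 and with the four-month minimum.)

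**Step 2: the SAP windows agree.** In SAP Table 3 the regimens without booster have 6- and 12-month immunogenicity windows. The regimens with booster do not: for the three-dose regimen the Day 113 window runs from day 100 to the end of Part A.

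**Step 3: the exception at 6 months.** Protocol 4.2.1 sets a minimum of 4 months since the last dose and no maximum. The booster entered the protocol with Amendment 4, dated 20 December 2021 (SAP 1). The synopsis estimates first enrolment in April 2021. Assuming 1 April 2021:
- Two-dose participants enrolled by 26 May 2021 reached D209 by 20 December 2021, before the booster was available.
- The first possible D265 visit in A2 is 21 December 2021.
- If A3 opened with Amendment 3 on 23 August 2021, its first D180 visit is 18 February 2022.

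Such participants could give a 6-month sample and be boosted afterwards, and SAP Appendix B, Step 1, would use that sample. The earliest 12-month visit is 29 April 2022, after Amendment 4, so the 12-month values come essentially from non-boosted participants.

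**Step 4: size of the distortion.** Let u be the share boosted before the late visit, N and T the 28-day geometric means in non-boosted and boosted participants, and r = N/T. The all-participant 28-day mean is T^u × N^(1−u), so

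N / all = (N/T)^u = r^u.

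The apparent late/28-day ratio is the true ratio in non-boosted participants multiplied by r^u. Neither u nor r is in the documents; all values below are assumed.

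| u | r = 0.5 | r = 1 | r = 1.5 | r = 2 | r = 3 |
|---|---|---|---|---|---|
| 0.25 | 0.84 | 1.00 | 1.11 | 1.19 | 1.32 |
| 0.5 | 0.71 | 1.00 | 1.22 | 1.41 | 1.73 |
| 0.7 | 0.62 | 1.00 | 1.33 | 1.62 | 2.16 |
| 0.9 | 0.54 | 1.00 | 1.44 | 1.87 | 2.69 |

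Example at u = 0.7: a true 4-fold fall shows as 4 / 1.62 = 2.5-fold if r = 2, and as 4 × 1.62 = 6.5-fold if r = 0.5. With the 28-day mean taken in the same participants, the factor is exactly 1 whatever u and r are.

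**The case against.** Several points on the other side are sound.

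- **No decay estimate is planned.** The protocol says "This study is designed for estimation purposes, and no between-group comparisons are planned", and no ratio of a late mean to the 28-day mean is specified. Each fold rise against Day 1 is within participants. This stands, and makes the problem one of presentation and interpretation rather than a biased test. But the 28-day and late fold rises are still averaged over different people, and a persistence objective invites the comparison.
- **Booster status is partly recognised.** SAP Table 3 separates regimens with and without booster, and SAP 6.1 allows separate analysis. This stands as far as it goes: the SAP permits the separation but does not commit to it.
- **Pre-booster titres are already reported.** A reader might infer that the BD-D1 sample serves only as a Part B baseline. It does not: SAP 3.3 lists its geometric means as Part B exploratory endpoints, and SAP 6.2.6 summarises the interval from last Part A dose to booster. Nor is BD-D1 a fixed 4-month time point, because the booster has no latest date.
- **Group A1.** The study-arm table (Protocol Table 2) gives A1 no Part B, so on that table the problem does not arise there. Other text points the other way: the synopsis offers the booster to all Part A participants, Table 7 footnote 3 covers A1, and SAP Table 3 has a column for two-dose unvaccinated participants with booster. That column may be meant for healthy adults only, but it does not say so.

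**Conclusion.** The concern holds in this form. The 12-month values, and most 6-month values once the booster is available on schedule, come from participants not boosted by that visit. They would be set beside 28-day means that by default include booster takers, with no committed comparison in the same people. The time course may therefore mix waning with selection.

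Two stronger readings are tempting but unsupported. One is that both late visits are observed only in people who declined the booster. Early enrollees can supply a 6-month value before a later booster, and not being boosted by a visit is not the same as declining. The other is that the decay is known to be distorted, by a given amount or in a given direction. That needs uptake to be related to titre, and the documents give neither. The factor r^u is 1 if they are unrelated, above 1 if non-boosted participants started higher (waning looks smaller), and below 1 if they started lower (waning looks larger). The tabulated range of 0.54 to 2.69 only illustrates assumed inputs.

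**What to change.** Amend SAP 6.4.3, with the matching sentence in SAP 6.1:

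- **(a)** For each 6- and 12-month geometric mean, report in the same participants the 28-day geometric mean and the within-participant fold change (late visit over 28 days), with 95% CIs and n.
- **(b)** Change *may* to *will* for the analysis by booster status, so that 28-day means are shown by booster status for every regimen that can enter Part B. Label 6- and 12-month results as participants not boosted by that visit.
- **(c)** As supportive information, show the already planned BD-D1 means by Part A regimen, with the paired 28-day mean and the actual interval since the last dose. Do not present BD-D1 as a fixed 4-month visit.

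Reconcile the passages on whether Group A1 can enter Part B (Protocol Table 2 against the synopsis, Table 7 footnote 3 and SAP Table 3).

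Pairing removes the change in composition from the late comparison. It does not show how boosted participants would have waned beyond their booster; (c) gives only partial information on that. The cost is SAP wording and table shells. All the samples are already scheduled.
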